This study aims to investigate the anti-inflammatory and anti-cancer properties of high-bioavailability curcumin in patients with mid-to-low rectal cancer undergoing neoadjuvant chemoradiotherapy. Curcumin is generally considered to have a high safety profile, and its oral formulation has been classified by the U.S. Food and Drug Administration (FDA) as “**Generally Recognized as Safe**” (GRAS) (GRAS Notice [GRN] No. 686). Reports of adverse effects related to curcumin are rare and primarily involve interference with bile secretion and iron metabolism.[1, 2] However, despite numerous molecular studies demonstrating curcumin’s anti-cancer and anti-inflammatory mechanisms, as well as its excellent oral safety, its oral bioavailability remains extremely low due to its lipophilic nature. Previous human studies have shown that even with oral administration of 12 grams of curcumin, the serum concentration only reaches 0.051 mg/mL[3], and approximately 75% of orally administered curcumin is excreted via feces.[4] The primary objective is to evaluate whether curcumin can reduce radiotherapy-associated adverse effects, such as radiation-induced enteritis, and improve the pathological complete response (pCR) rate to chemoradiotherapy. In addition, translational research will be conducted on tumor tissue samples collected at different time points to elucidate the underlying molecular mechanisms.

Investigational product(s) :

High-Bioavailability Curcumin (BCM95 curcumin)

Development Phase : I II III IV 其它 _____ 不適用

Study Design :

1. Experimental Group

Control Group : Placebo
 Study Drug (Name、Dose、Usage) _____
 Other _____

2. Blinding : Open Evaluator-blind Single-blind(patient) Double-blind(patient+PI)
 Double Dummy Other _____

3. Randomization: Yes No

4. Parallel design Crossover design Other single arm Not applicable

5. Treatment Period : 5 months Not applicable

6. Study Period: 3 years (or From 2026/01/01 to 2029/12/31)

6. Dose adjustment : Mandatory Selectively No Not applicable

7. Study location : Single Multi-center Global

Endpoints (Outcome measure) :

1. Primary endpoint:

1. **Grade 3 enteritis/proctitis** or grade 3 GI AE: evaluated by National Cancer Institute Common

- (C) Patients does not receive radiotherapy
- (D) Unable to receive further curative resection
- (E) Patients receive tumor resection before the neoadjuvant treatment
- (F) Patients have history of more than 5 Gy of pelvic radiation
- (G) Patients in pregnancy or lactation status
- (H) Patients have allergic history to curcumin, 5-fluouracil or oxaliplatin
- (I) Patients of childbearing potential can not cooperate with appropriate contraceptive method (oral, injectable, or implantable hormonal contraceptive; tubal ligation; intra-uterine device; barrier contraceptive with spermicide; or vasectomized partner)
- (J) Patients with any concurrent malignancy; patients with history of malignancy should be cancer-free for more than 5 years
- (K) Patients with New York Heart Association (NYHA) class III or IV heart failure, unstable angina pectoris, unstable cardiac arrhythmia or tachycardia (heart rate > 100 beats/minute)
- (L) Patients have concurrent uncontrolled medical conditions, such as illness ongoing or requiring IV antibiotics, severe chronic renal failure (eGFR <30 mL/min/1.73m²) or severe active hepatitis(ALT>3x upper normal limit) 、 Total Bilirubin>2 mg/dl
- (M) Patients with previous or current drug abuse
- (N) Patients underwent major surgery within 28 days of study enrollment (except diverting colostomy)
- (O) Patients have Familial Adenomatosis Polyposis Coli (FAP), Hereditary Non-Polyposis Colorectal Cancer (HNPCC), active Crohn's disease or active ulcerative Colitis
- (P) Patients have known dipyrimidine dehydrogenase deficiency (DPD)
- (Q) Patients with congenital iron metabolic or hematopoietic diseases
- (R) Patients with synchronous colon cancer

(S) The Patients with hematologic abnormalities (INR > 1.5, white blood cell (WBC) count < 3,000/ μ L, absolute neutrophil count (ANC) < 1,500/ μ L, platelet count < 100,000/ μ L, hemoglobin < 9.0 g/dL not caused by tumor treatment) or known hematologic diseases (aplastic anemia, myelodysplastic syndrome (MDS), leukemia, malignant lymphoma, multiple myeloma, hereditary hematologic diseases such as thalassemia, sickle cell anemia, etc.).

- (T) The patient has diabetes mellitus

(U) The patient is taking the immunosuppressants Cyclosporine, Tacrolimus, Sirolimus, and Everolimus and anticoagulants (warfarin 、 NOACs 、 aspirin)

For translational analyses, only residual clinical specimens (e.g., a few millimeters of surplus tumor tissue) obtained after standard diagnostic or therapeutic procedures will be utilized. The sampling volume is minimal and will not interfere with diagnostic interpretation. All specimens will be de-identified and coded in accordance with ethical and regulatory standards and will be used exclusively for translational and biomarker studies.

Sample size calculation is performed using one proportion equality test using the exact test to achieving an 80% power at the 5% level of significance. With the expectation of an -15% of improvement of acute radiation proctitis (30% to 15%), the total estimated patients number in a single-arm trial required is 64. Consider the patient with incomplete data and drop-out rate of 10%, the total estimated number of sample size is 72. Sample size calculation was performed using PASS software (Power Analysis and Sample Size version 2021, NCSS, Kaysville, Utah, USA).

Concomitant Treatments : 不適用

1. Concomitant Therapy :

1.1 TEGAFOX(one cycle):

*Oxaliplatin 85 mg/m² in D5W 250 ml IVF 2 hrs, D1, every 2 wks

*Tegafur-uracil 300mg/m²/day and leucovorin 90mg/day PO, given on days 1 to 5 and 8 to 12 days, every 2 weeks

1.2 FOLFOX(one cycle):

*Oxaliplatin 85 mg/m² in D5W 250 ml IVF 2 hours, D1

*Calcium Folinate 100 - 400 mg/m² in D5W 250ml IVF 2 hours, D1

*5-FU 400 mg/m² IV bolus on D1 *5-FU (2400 mg/m²) IVF 46 hrs, Repeat every 2 weeks

1.3 UFUR (one cycle)

*Tegafur 300-350 mg/m²/day and leucovorin 90mg/day PO on day 1 to day 5, then rest for 2 days for 2 weeks

1.4 The radiation therapy modules are as follows:

Short-Course (hypofractionated, 25 Gy/5 fractions) Radiotherapy (SCRT)

2. Prohibited Therapy : cell therapy, immunotherapy

Statistical Methods :

1. Main study Hypothesis : Equality Superiority Non-inferiority
 Equivalence Other

2. Estimated Sample Size : 整個試驗預計納入人數_72_，整個試驗可評估人數_64_
 本中心預計納入人數_72_，本中心可評估人數_64_

3. Efficacy assessment group : Intent-to-treat (ITT) Per-Protocol (PP)
 Other _____

附註：意圖治療：Intent-to-treat (ITT)；依計畫書：Per-Protocol (PP)

4. Interim analysis : Yes No

5. Statistical methods : descriptive statistics, Kaplan-Meier method, T-test

6. Handling of Missing Data : Listwise deletion

2. Introduction and Rationale

The primary treatment method for non-metastatic locally advanced rectal cancer is TME (Total mesorectal excision). In recent years, neoadjuvant chemotherapy and radiation therapy have been proven to decrease local recurrence and increase the possibility of organ preservation. [5, 6] However, radiation proctitis is a joint adverse event in one-third of patients one week after radiation treatment is complete; [7] and severe acute toxicity was observed in 4.2% of patients. [8]

Curcumin (diferuloylmethane) is a hydrophobic polyphenol derived from the rhizome of *Curcuma longa*. It has been proven an anti-inflammatory agent as an NF- κ B inhibitor [9] and has numerous intrinsic and extrinsic anti-neoplastic pathways. [10] The murine model showed that oral curcumin could alleviate irinotecan-induced intestinal injury via attenuation of NF- κ B activation, oxidative stress and endoplasmic reticulum stress. [11] One phase I clinical trial showed the oral form curcumin can be safe even up to 8 gram per day. [12] Moreover, the USFDA has designated oral curcumin as a “generally recognized as safe” agent. (US FDA; per 21 CFR 182.10, 182.20) However, due to its hydrophobic feature, poor bioavailability limited its clinical application. [13]

BCM-95® contains an extract characterized as a 95% curcuminoid complex (curcumin, demethoxycurcumin, and bisdemethoxycurcumin in their natural ratios) along with turmeric essential oil. The bioavailability of BCM-95® has been proven to be 6.93-fold compared to regular curcumin. [14] Therefore, the application of BCM-95® may improve radiation-related inflammation and chemotherapy-induced mucosal injury. Moreover, its anti-neoplastic effect may improve the tumor response to current neoadjuvant therapy and therefore improve the long-term outcome of rectal patients.

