5.3 Withdrawal criteria

Subject should be withdrawn from the study due to any of the following conditions:

1. The subject voluntarily decides to withdraw her/his consent
2. The subject dies or is lost to follow-up
3. The subject is pregnancy
4. The subject develops disease progression (metastasis or enlargement confirmed)
5. Any clinical adverse event, laboratory abnormality, intercurrent illness, or any occurrence or change in the subject's physically and/or psychologically status giving indication to the investigator that further participation in the study may not be the best interest of the subject
6. The subject does not receive, or is unable to receive, the study intervention, does not keep appointments, or otherwise does not adhere to protocol requirements
7. The subject was enrolled by error and/or it is discovered that the subject does not meet the eligibility criteria after enrollment
8. The study is terminated prematurely by the investigator, research institution, sponsor, IRB or regulatory authorities

For a subject who is withdrawn due to progress confirmed, CT (or MRI) and colonoscopy could be waived at the Early Termination Visit per the investigator's judgments. If a subject is discontinued due to an AE, every effort will be made to follow the event until event resolves or stabilizes at a level acceptable to the investigator.

6. Treatments

6.1.Treatment Administration

A daily dose or high bioavailability curcumin (BCM-95 curcumin) 3g per day is given orally along with the neoadjuvant short-course radiation therapy and chemotherapy.

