9.1 Definitions and reports of Adverse Events

All adverse events that occur after the informed consent is signed (including run-in) must be recorded on the adverse event CRF (paper and/or electronic) whether or not related to study agent. AE Data Elements including:

- AE reported date
- AE Verbatim Term
- CTCAE Term (v 5.0)
- Event onset date and event ended date
- Severity grade
- Attribution to study agent (relatedness)
- Whether or not the event was reported as a Serious Adverse Event (SAE)
- Action taken with the study agent
- Outcome of the event
- Comments

Identify the adverse event using the NCI Common Terminology Criteria for Adverse Events (CTCAE) version 5.0. The CTCAE provides descriptive terminology and a grading scale for each adverse event listed.

AEs will be assessed according to the CTCAE grade associated with the AE term. AEs that do not have a corresponding CTCAE term will be assessed according to their impact on the participant's ability to perform daily activities as follows:

Grade	Severity	Description
1	Mild	
• Barely noticeable, does not influence functioning• Causing no limitations of usual activities
2	Moderate	
• Makes participant uncomfortable, influences functioning• Causing some limitations of usual activities
3	Severe	
• Severe discomfort, treatment needed• Severe and undesirable, causing inability to carry out usual activities
4	Life threatening	
• Immediate risk of death• Life threatening or disabling

5	Fatal	• Causes death of the participant
---	-------	-----------------------------------

The possibility that the adverse event is related to study drug will be classified as one of the following: not related, unlikely, possible, probable, definite.

DEFINITION of Serious Adverse Events: ICH Guideline E2A and GCP of Taiwan define serious adverse events as those events, occurring at any dose, which meet any of the following criteria:

- Results in death
- Is life threatening (Note: the term life-threatening refers to an event in which the patient was at risk of death at the time of the event; it does not refer to an event which hypothetically might have caused death if it were more severe).
- Requires inpatient hospitalization or prolongation of existing hospitalization
- Results in persistent or significant disability/incapacity
- Is a congenital abnormality/birth defect

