11.1 Sample size Determination

Sample size calculation is performed using one proportion equality test using the exact test to achieving an 80% power at the 5% level of significance. With the expectation of an -15%

of improvement of acute radiation proctitis (30% to 15%), the total estimated patients number in a single-arm trial required is 64. Consider the patient with incomplete data and drop-out rate of 10%, the total estimated number of sample size is 72. Sample size calculation was performed using PASS software (Power Analysis and Sample Size version 2021, NCSS, Kaysville, Utah, USA).

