11.2.5.1 Procedure for accounting for missing, unused and spurious data

The incomplete clinical data and sequencing data with poor quality will be excluded in the study.

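### Listwise deletion has no exemption for the primary endpoint and, under the section 3.2.1 wording, could drop patients whose GI toxicity is already recorded

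*Protocol*

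**What the plan says.** - **Missing data.** Synopsis, Statistical Methods, item 6: "Handling of Missing Data : Listwise deletion". Section 11.2.5.1: "The incomplete clinical data and sequencing data with poor quality will be excluded in the study". Neither place makes an exception for the primary endpoint.
- **Sample size.** Section 11.1 plans 64 evaluable patients for a fall from 30% to 15%, then adds an allowance: "Consider the patient with incomplete data and drop-out rate of 10%, the total estimated number of sample size is 72".
- **Primary endpoint.** The synopsis defines it through grade 3 enteritis/proctitis or grade 3 GI adverse events and cumulative GI symptoms, and lists the Vienna Rectoscopy Score as secondary. Section 3.2.1 names CTCAE grading together with a colonoscopy 2 weeks after radiotherapy. Section 7 has symptoms recorded 2 to 4 weeks after radiotherapy and gives the colonoscopy its own sentence.
- **Withdrawal (section 5.3).** Item 5 covers an adverse event "giving indication to the investigator that further participation in the study may not be the best interest of the subject". Item 6 reads: "The subject does not receive, or is unable to receive, the study intervention, does not keep appointments, or otherwise does not adhere to protocol requirements".
- **Records that survive withdrawal.** Section 9.1: "All adverse events that occur after the informed consent is signed (including run-in) must be recorded on the adverse event CRF". Section 5.3: "If a subject is discontinued due to an AE, every effort will be made to follow the event". The same section says that "CT (or MRI) and colonoscopy could be waived at the Early Termination Visit", but only for patients withdrawn for progression.

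**The concern.** The event being counted can itself cause the data to be incomplete. A patient with severe proctitis may decline the colonoscopy, miss visits or be withdrawn. If that patient then counts as incomplete and is deleted, an event leaves the numerator although it is on file. In a randomised trial the control arm would undergo similar deletion. Here the comparison is with a fixed 30% rate, so nothing offsets the loss, and the observed rate moves towards benefit.

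The protocol requires adverse events to be recorded and followed, but does not say that a recorded event keeps the patient in the primary rate. This goes beyond a detail left to an analysis plan, because the protocol itself states the deletion rule twice.

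**Working it through.** **1. The plan's own figures.** p0 = 0.30 and p1 = 0.15 (section 11.1), two-sided 5% (section 11.2), power 80%. By the normal approximation:

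n = [(1.960·√(0.30·0.70) + 0.8416·√(0.15·0.85)) / 0.15]² = 63.86, rounded up to 64. Then 64/0.9 = 71.1, rounded up to 72. Both stated numbers reproduce.

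**2. Decision limits.** With an exact binomial test against 30% and a lower tail of 2.5%, benefit is claimed at:
- 11/64 or fewer (tail 0.0145; power at 15% is 75.4%);
- 13/72 or fewer (tail 0.0155; power 81.6%). At 14/72 the tail is 0.0303, so there is no claim.

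**3. False-claim rate under listwise deletion.** Assume a true rate of 30%, 72 enrolled, an overall missing fraction m, and event patients r times as likely to be missing. Then:
- P(missing | no event) = m / (0.7 + 0.3r), and P(missing | event) is r times that;
- expected observed rate = 0.30·(1 − P(missing | event)) / (1 − m).

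Example, m = 5%, r = 3: 0.05/1.6 = 0.03125; times 3 = 0.09375; 0.30 × 0.90625/0.95 = 28.6%.

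The false-claim rate sums over the number of patients remaining, with the exact limit recomputed for each:

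| Missing | r = 1 | r = 2 | r = 3 | r = 5 |
|---|---|---|---|---|
| 3% (assumed) | 1.75% | 2.16% | 2.46% | 2.86% |
| 5% (assumed) | 1.68% | 2.41% | 2.98% | 3.82% |
| 10% (plan's full allowance) | 1.70% | 3.48% | 5.25% | 8.27% |

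The nominal 2.5% is passed only at r = 5 with 3% missing, at r = 3 or more with 5%, and at r = 2 or more with 10%. The table treats all missing patients alike. A rule that counts recorded events removes only the part of the bias due to deleted patients whose event is on file.

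**4. Tipping point at the full allowance (8 deleted).** A claim at 11/64 is lost if 3 of the 8 had the event, since 11 + 3 = 14/72. A claim at 10/64 is lost if 4 did, and at 9/64 if 5 did. The design rate of 15% gives 9.6 expected events in 64.

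**5. A repair that would be worse.** If all 72 stay in the denominator and unassessed patients are silently taken as non-events, the false-claim rate at 10% missing is 5.3%, 9.5%, 13.2% and 18.8% for r = 1, 2, 3 and 5. Each exceeds the listwise figure in the table.

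**The case against.** Listwise deletion removes cases whose analysed value is missing. A patient with a grade 3 event on the adverse event form has a value, and under the synopsis wording, which has no colonoscopy component, that record should be enough. Withdrawal ends participation; section 5.3 does not say that data already collected are discarded. Adverse events are to be assessed every two weeks and followed after discontinuation, and the waiver of colonoscopy is limited to progression. All of this stands. It confines the problem to the section 3.2.1 wording and to a broad reading of section 11.2.5.1.

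The size can also be challenged. The schedule places the first adverse event evaluation and post-radiotherapy colonoscopy at week 3 ± 1, whereas the 10% allowance has no stated timing in a course of about 19 weeks. Missing data by the time of assessment may therefore be well below 10%. No text supports any particular ratio r, and withdrawals for progression or consent need not act in one direction. Section 2 cites severe acute toxicity of 4.2%. At that rate about 3 of 72 patients would have events (0.042 × 72 = 3.0), and deletion could not change the conclusion. These points also stand.

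A reader might infer that the plan discards the events of every withdrawn patient, or that false claims of 8% or more are to be expected. The documents support neither: the first is written nowhere, and the second needs the full 10% missing together with a strong assumed link to toxicity.

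The choice of intent-to-treat or per-protocol cannot be read in the text available. If intent-to-treat is ticked, it still has to be reconciled with listwise deletion.

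**Conclusion.** The concern holds in a limited form. The protocol fixes a deletion rule that, under one of its own endpoint wordings, permits a patient with a recorded qualifying event to be left out of the primary rate. The bias from such deletion is towards benefit. Its size is unknown and probably small: at 3% to 5% missing and r between 2 and 5, the false-claim rate is 2.2% to 3.8%, against about 1.7% if missing at random. These figures rest on a true rate of 30%, an exact two-sided 5% test, and assumed values of m and r. The change is worth making because it costs almost nothing and the records it needs are already required.

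**What to change.** For the primary endpoint, state that:
1. any patient who starts study radiotherapy and has a qualifying event on the adverse event form within the endpoint's assessment period counts as an event, whether or not the patient was withdrawn or the colonoscopy is missing;
2. a patient counts as a non-event only if a toxicity assessment in that period shows none;
3. patients with neither a recorded event nor an assessment are left out of the main rate, with their number and reasons reported, and one sensitivity analysis counts them all as events;
4. this overrides section 11.2.5.1 and, for this endpoint, item 6 of the synopsis.

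Reconcile the primary endpoint and its assessment period across the synopsis, section 3.2.1 and section 7, including whether colonoscopy is a component. Section 7's 4 weeks should not become a cut-off by default, since the synopsis endpoint carries no such limit.

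The cost is wording and one short analysis; no visit or procedure is added. The observed rate may look slightly less favourable. The all-events analysis is harsh and should remain a sensitivity analysis. With 2, 4 or 8 patients unassessed it supports benefit only at 11/70, 9/68 or 5/64 observed events or fewer. At a true 15% that happens with probability 64%, 42% or 7%, against 84%, 79% or 75% for the analysis of assessed patients.

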1.3 UFUR (one cycle)

*Tegafur 300-350 mg/m²/day and leucovorin 90mg/day PO on day 1 to day 5, then rest for 2 days for 2 weeks

1.4 The radiation therapy modules are as follows:

Short-Course (hypofractionated, 25 Gy/5 fractions) Radiotherapy (SCRT)

2. Prohibited Therapy : cell therapy, immunotherapy

7. Efficacy Assessments

1. **Grade 3 enteritis/proctitis**: evaluated by National Cancer Institute Common Terminology Criteria for Adverse Events Version 5.0 (NCI CTCAE v. 5.0) and the criteria of the Radiation Therapy Oncology Group (RTOG) and European Organization for Research and Treatment of Cancer (EORTC). The sign or symptoms of radiation proctitis (diarrhea, rectal bleeding, rectal pain) is evaluated and recorded by our research nurse 2 to 4 weeks after radiation therapy completed. Colonoscopy evaluation for Vienna Rectoscopy Score will take place 2 to 3 weeks after the radiation therapy is completed.
2. Any grade III adverse events during the neoadjuvant therapy: evaluated by clinicians according to National Cancer Institute Common Terminology Criteria for Adverse Events Version 5.0 (NCI CTCAE v. 5.0) every cycles of chemotherapy. An additional evaluation and record will be recorded by the research nurse every 3 cycles of chemotherapy.
3. Clinical complete response rate of the primary tumor after completion of the neoadjuvant treatment: evaluated by Response Evaluation Criteria in Solid Tumors Version 1.1 (RECIST v1.1) after neoadjuvant chemotherapy and radiation therapy completed
4. Pathological or clinical complete response rate of the primary tumor after completion of the neoadjuvant treatment: defined as no residual cancer cells in the resected specimen after curative resection
5. Patient's tolerability and completion rate of the neoadjuvant therapy

8. Safety Assessments

The complete blood count is evaluated on each admission for chemotherapy. The adverse events is evaluated according to National Cancer Institute Common Terminology Criteria for Adverse Events Version 5.0 (NCI CTCAE v. 5.0). Serum creatinine, electrolyte, AST, ALT, total and direct bilirubin is examined on each 3 cycle of chemotherapy.

If ALT or AST exceeds three times the upper limit of normal (3×ULN), curcumin administration will be suspended. This 3×ULN threshold is a commonly used warning indicator for drug-induced liver injury. In such cases, we will monitor liver function tests weekly until the values recover to <1.5×ULN or return to baseline.

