11.2.1 Efficacy analysis

Adverse events are assessed by the clinician on each cycle of admission, and additional record of adverse events (CTCAE version 5) by our research nurse on every 3 cycles of chemotherapy.

Clinical complete remission is evaluated on each colonoscopy examination after the neoadjuvant chemotherapy and radiation therapy completed according to Response Evaluation Criteria in Solid Tumors Version 1.1 (RECIST v1.1). In addition, the pathologist evaluates pathological complete response and tumor regression grade after curative resection.

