11.2.5 Analysis Population

The outcome of this single arm clinical trial is compared with other clinical trials and our previous retrospective neoadjuvant chemoradiation data of CGMH.

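### Listwise deletion, read as written, can drop patients withdrawn for progression from the complete-response denominator and modestly overstate that secondary endpoint

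*Protocol*

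**What the plan says.** **Missing data.** The synopsis, under Statistical Methods item 6, gives one rule: "Handling of Missing Data : Listwise deletion". Section 11.2.5.1 adds: "The incomplete clinical data and sequencing data with poor quality will be excluded in the study". Neither place limits the rule to particular endpoints.

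**When response is scored.** Section 7, item 3, has clinical complete response "evaluated by Response Evaluation Criteria in Solid Tumors Version 1.1 (RECIST v1.1) after neoadjuvant chemotherapy and radiation therapy completed". Section 11.2.1 agrees: "Clinical complete remission is evaluated on each colonoscopy examination after the neoadjuvant chemotherapy and radiation therapy completed". The combined pathological-or-clinical rate is defined in sections 3.2.2 and 7 by the resected specimen.

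**Who leaves the study first.** Section 5.3 lists as a withdrawal criterion: "The subject develops disease progression (metastasis or enlargement confirmed". It continues: "For a subject who is withdrawn due to progress confirmed, CT (or MRI) and colonoscopy could be waived at the Early Termination Visit", at the investigator's judgment.

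**How the result is used.** Section 11.2.5: "The outcome of this single arm clinical trial is compared with other clinical trials and our previous retrospective neoadjuvant chemoradiation data of CGMH".

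**Analysis set.** Synopsis Statistical Methods item 3 prints both an intent-to-treat and a per-protocol option. The tick cannot be read in the text available to us.

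**The concern.** A patient whose primary tumour is confirmed to have enlarged during treatment has not had a complete response. That outcome is known. Yet the endpoint is scored only at a later time, which this patient does not reach in the study, and the examinations that could document the outcome at the exit visit may be waived. The cell for complete response is then empty, and the stated handling of an empty cell is deletion. No readable text in the protocol says that progressors or unassessed patients count as non-responders.

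Deleting patients who did not respond can only raise the observed response rate. The trial has one arm and is read against other trials and the centre's retrospective data, so no concurrent control arm is subject to the same loss. What is at stake is an optimistic estimate of a secondary endpoint, not a wrong pass-or-fail decision, because the protocol ties no success rule to complete response.

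**Working it through.** **Step 1. Does the text lead to deletion?**

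| Element | Where | Consequence for a confirmed progressor |
|---|---|---|
| Response scored after therapy is completed | Sections 7 (item 3), 11.2.1 | Not reached within the study |
| Withdrawal on confirmed progression | Section 5.3 | Leaves the study before that assessment |
| CT/MRI and colonoscopy may be waived at exit | Section 5.3 | Possibly no substitute assessment |
| Listwise deletion; incomplete clinical data excluded | Synopsis item 6; section 11.2.5.1 | Can be removed from the denominator |

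The chain is possible at every link, but not compulsory: the waiver is optional, and an analyst could record progression as non-response.

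**Step 2. The plan's own figures.** Sections 4.2 and 11.1 give 64 evaluable patients and a 10% allowance for incomplete data and drop-out. 64 / 0.90 = 71.1, rounded up to 72, which reproduces the planned enrolment. The allowance is 72 − 64 = 8 patients. We use 8 as an upper bound, since it supposes that every lost patient is a deleted non-responder.

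**Step 3. Size of the effect on clinical complete response.** With r responders among 72 and d non-responders deleted:

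- rate in all patients = r / 72
- rate after deletion = r / (72 − d)
- ratio of the two = 72 / (72 − d)

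The ratio is 1.014, 1.029, 1.059 and 1.125 for d = 1, 2, 4 and 8. The protocol states neither a complete-response rate nor a progression rate, so r and d are assumptions:

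| r (assumed) | All 72 | d = 2 | Change, points | d = 8 | Change, points |
|---|---|---|---|---|---|
| 11 | 15.3% | 11/70 = 15.7% | +0.4 | 11/64 = 17.2% | +1.9 |
| 18 | 25.0% | 18/70 = 25.7% | +0.7 | 18/64 = 28.1% | +3.1 |
| 22 | 30.6% | 22/70 = 31.4% | +0.9 | 22/64 = 34.4% | +3.8 |

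**Step 4. Comparison with sampling error.** The 95% half-width at n = 72 is 1.96 × √(p(1 − p)/72). At p = 0.153 it is about 8 points and at p = 0.306 about 11 points. The shift is small beside this. Unlike sampling error, however, it goes only one way when the deleted patients are non-responders.

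**Step 5. The combined pathological-or-clinical rate.** Watch-and-wait patients have no resected specimen, so the same rule could delete them too, and they may include clinical complete responders. The net direction for the combined rate is therefore not fixed by the documents, and the table applies to the clinical rate only.

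**The case against.** The strongest reply is that listwise deletion acts on missing values, and confirmed progression is not a missing value. Section 4.3 also schedules colonoscopy at weeks 3, 11 and 19, so tumour status is examined during treatment. Moreover, an intent-to-treat tick in the synopsis would keep all patients in. Finally, response denominators are often left to an analysis plan, which we do not have.

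Part of this stands. A sensible analyst might well score progressors as non-responders. But the protocol defines the endpoint by an assessment after therapy and then states a deletion rule without exception, so this is a stated rule and not silence. An intent-to-treat tick would contradict listwise deletion and need reconciling with it; it would not cure the problem.

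A reader might also infer more than the documents support:

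- **That every progressor is a known non-responder.** The endpoint concerns the primary tumour. Confirmed enlargement of it settles the matter; metastasis alone does not. Such a patient only lacks a documented complete response.
- **That all withdrawn patients are lost in the same way.** Section 5.3 also withdraws a patient who "does not keep appointments, or otherwise does not adhere to protocol requirements", and patients with certain adverse events. The waiver covers confirmed progression only, and some of the others may finish therapy and respond.
- **That the completion rate is inflated, even to 100%.** A true 64/72 = 88.9% would read 64/64 = 100% if all 8 non-completers were deleted. But a patient who stopped early has a known completion status, so this needs the strained reading that withdrawal itself makes the record incomplete.
- **That the primary toxicity rate is biased.** Adverse events are recorded from consent (section 9.1), assessed every two weeks (synopsis, Study Procedures) and followed after discontinuation for an adverse event (section 5.3). The documents show no direction of bias there.
- **That the external comparison is necessarily unfair.** Section 11.2.5 does not say how the comparison data treat unassessed patients; they may share the same omission.

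**Conclusion.** The point holds for complete response. The missing-data rule, the timing of the endpoint and the withdrawal provisions together can remove treatment failures from the denominator, and so overstate the clinical complete response rate. On assumed true rates of 15.3% to 30.6%, the overstatement is about 0.4 to 0.9 points with 2 non-responders deleted and 1.9 to 3.8 points at the upper bound of 8. It is nil if no such patient arises or if the investigators obtain and score an assessment. This is worth correcting because the rule is stated and the correction is cheap, but it threatens neither the primary analysis nor a formal decision.

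**What to change.** For complete response, replace listwise deletion with the following:

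1. The denominator is all eligible patients who start protocol radiotherapy.
2. Confirmed progressors, and patients with neither a clinical nor a pathological response assessment, count as not having a complete response.
3. Watch-and-wait patients are classified by their clinical assessment.
4. The complete-case rate is reported as a sensitivity analysis.

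State that a patient who stops early counts as a non-completer in the completion rate and is not missing data. Keep listwise deletion for the sequencing and biomarker data only. Confirm which analysis set is ticked in the synopsis and, if it is intent-to-treat, reconcile items 3 and 6. The primary endpoint needs no change beyond saying that recorded qualifying events count in patients who are later withdrawn.

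The cost is protocol wording and one extra analysis. The reported response rate may be slightly lower, and scoring unassessed patients as non-responders may understate response if some of them did respond; the complete-case rate shows how much this matters.
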